# 2.2. A SUMMARY OF CLINICAL DATA

Cenegermin has previously been studied in healthy volunteers and in different subject populations. In the completed Phase I study in healthy volunteers (study **CCL**), a total of 58 subjects (out of 74 enrolled) were treated with single and multiple doses of different concentrations of cenegermin ophthalmic solution showing a good safety profile.

Furthermore, a Phase I/II multicenter, double-masked, vehicle-controlled study evaluating the safety and efficacy of cenegermin at 10 and 20 mcg/mL six times a day in 174 patients with stage 2 and 3 of Neurotrophic Keratitis (CCI ) was completed in 2015; the study demonstrated that cenegermin was very well tolerated and effective in patients with NK. A successful confirmatory study (CCI ) was completed in 2016 and marketing authorization for cenegermin 20 mcg/mL ophthalmic solution was granted by the EMA in July 2017 for treatment of moderate to severe NK. While in the US cenegermin was approved by FDA in 2018 for all stages of Neurotrophic Keratitis. Cenegermin is distributed under the trade name Oxervate® 20 mcg/mL ophthalmic solution.

In addition to NK, cenegermin ophthalmic solution has been evaluated in a Phase I/II study in retinitis pigmentosa patients at 60 and 180 mcg/mL dosages (CCL)), and in a phase I/II study in glaucoma at a dose of 60 mcg/mL (CCL)). An open label, uncontrolled study showed that 4 weeks treatment with cenegermin ophthalmic solution at 20 mcg/mL and 4 mcg/mL concentrations was safe and effective in improving symptoms, corneal staining and tear production in patients with dry eye disease (CCL)). These results prompted two additional phase II randomized clincat trials in patients with DED (CCL)) and in those with ocular discomfort symptoms following refractive surgery (CCL); these also confirmed the favourable tolerability profile of cenegermin ophthalmic solution at a concentration of 20 mcg/mL when used up to 6 times daily for 8 weeks.

In the double-masked vehicle-controlled Phase II study **CC** no major differences were observed in efficacy when comparing the two administration regimens (6 vs. 2 times/day) and treatment durations (8 weeks vs. 4 weeks) in a subset of patients with similar characteristics (hyposecretive dry eye with Schirmer test <10mm/5min).

An additional phase II study (CCL)) was specifically designed to further prove this hypothesis. It was a 4 week, Phase 2, multicenter, randomized, double-masked, vehicle-controlled, parallel group study with 12 weeks of follow-up to evaluate safety and efficacy of cenegermin ophthalmic solution versus vehicle, in patients with moderate to severe dry eye, started in 2018 in patients with hyposecretive dry eye (with or without an evaporative component caused by the reduced tear film), including patients diagnosed with primary Sjogren syndrome.

In this phase II trial a total of 261 patients were randomized 1:1:1 to receive either cenegermin ter in die (TID) (i.e. 3 times/day), or cenegermin bis in die (BID - i.e. 2 times/day), or vehicle.

The primary endpoint of the study was the change from baseline in Schirmer I test (without anaesthesia), while key secondary endpoints included change from baseline in SANDE scores for severity and frequency, cornea and conjunctiva vital staining, TFBUT and quality of life. Despite the primary endpoint at p<0.025 was not reached in the overall population, the study has clearly shown a superior efficacy of both cenegermin arms versus placebo, especially considering that due to the Covid-19 emergency recruitment was interrupted when only 261 (the minimum number required) out of the 300 patients initially planned were randomized. However, when analyzing the percentage of patients achieving more than 10 mm in Schirmer I test scores at the end of treatment, as pre-specified in the statistical analysis plan (SAP), the difference between both cenegermin dose regimens vs. placebo was statistically significant for both study groups (p=0.028 for cenegermin TID and p=0.007 for cenegermin BID [P-value versus Vehicle TID based on Fisher's exact test]). It is notewhorty that, while no clear dose ranging effect was observed on the tear function endpoints, symptoms recorded by the DE-specific and validated SANDE questionnaire showed a significant persistence of the beneficial effect of the higher dose-regimen (TID) over time and up to the full 16 weeks after the end of the 4 weeks treatment

cycle. In fact, statistical significance vs. vehicle was reached at all follow-up timepoints for the TID with best result at week 12 (p=0.002 based on t-test; missing data imputed by LOCF). In addition, no difference was observed in the safety and tolerability profile of the experimental treatment. Specifically, up to 3 instillations per day of cenegermin ophthalmic solution in both eyes confirmed to be safe and well tolerated. The two cenegermin study groups have shown a similar tolerability. No serious adverse events were reported in the study. Adverse reactions were mild and transient, and occurred only during the 4-weeks treatment period of the 16-weeks cycle.

The results of these three randomized controlled studies in DED patients, as well as the results on reflex tear secretion obtained in the neurotrophic keratitis trials **CCL** and **CCL**, suggests that cenegermin may be a safe and effective treatment option for patients with hyposecretive/aqueous tear-deficient dry eye disease. In all studies rhNGF was well tolerated and the reported ocular AEs were generally transient and mostly mild and moderate in intensity during the controlled treatment period and the follow-up period.

In the Phase I, randomized, double-masked, placebo-controlled study to evaluate the safety, tolerability and pharmacokinetics of rhNGF eye drops in healthy volunteers of Japanese ethnicity (study **CCL**), a total of 30 subjects were enrolled. Twenty subjects were treated with a single dose of cenegermin ophthalmic solution at a 20 mcg/mL concentration and a total of 10 subjects were treated with vehicle. On day 1 patients received only one dose of cenegermin, then the remainder of the trial they received one drop six times a day. Both the single and multiple doses of cenegermin delivered topically as ophthalmic solution were safe and well tolerated by healthy subjects of Japanese ethnicity. No clinically important changes in ECG were observed after dosing with cenegermin. There was no apparent relationship between treatment and plasma cenegermin levels, and this study did not give any indication for an immunogenic potential of cenegermin in humans after ophthalmic treatment.

# 2.3. STUDY RATIONALE

The data reported above, together with the evidence of cenegermin ophthalmic solution effectiveness in the treatment of patients affected by corneal epithelial defects and ulcers, and moderate to severe DE make cenegermin a strong candidate for the treatment of severe Sjogren's DED.

NGF addresses the neurosensory abnormalities associated with DE that are pivotal to restoring ocular surface homeostasis and tear film stability. Sjogren's DE is a complicated consortium of clinical characterics driven by many factors, and most patients are on chronic topical therapy. Additionally, as noted previously, the pathogenesis of DE is multifactorial, and while NGF potentially affects many of these mechanisms. CD4+ T cell-mediated inflammation has been well established to play a role in dry eye disease. Various studies have demonstrated that in patients with DE there are increased levels of CD4+ T cells and inflammatory mediators such as IL-6, TNF-a, IL-2, IFN- $\gamma$  and IL-17 in the tears and conjunctiva. The inflammatory component of DE is believed to drive symptoms in these patients, which is typical why you see patients on various topical medications targeting various pathways. Topical CsA is an immunomodulatory calcineurin-inhibitor that blocks T cell infiltration, activation, and thus, the downstream release of pro-inflammatory mediators including cytokines and chemokines that are involved in the pathogenesis of dry eye. The utilization of NGF in Sjogren's DE patients in conjunction with chronic treatment with topical CsA could represent an approach targeting the different mechanisms of the disease.

Additionally, The T cell inhibiting function of CsA is thought to be the key driver for symptomatic relief in patients with DED. In a survey of 5,884 patients, a statistically significant reduction in symptom severity was observed after treatment. Interestingly, mixed results have been reported regarding CsA improvement in the signs of DE. For example, even though CsA 0.05% emulsion is indicated to increase tear production, lack of replication in individual pre-specified primary efficacy endpoints between the two Phase III trials. This coincides with a review of 30 randomized control trials with a total of 4009 participants and follow-up periods ranging from 6 weeks to 12 months on the effectiveness of CsA, both 0.05% and 0.09%, in the treatment of DE by de Paiva et al. The authors concluded that the evidence as to whether or not CsA provides benefit for tear production was inconsistent and of low certainty. As summarized above, CsA can improve symptoms but does not significantly impact tear production. Therefore, the efficacy of NGF in this study will be primarily assessed by evaluating sign of dry eye through tear production (Schirmer 1). Since the patients enrolled have severe disease with significant lacrimal insufficiency, we cannot physiologically expect an increase of 10mm or more in Schirmer I scores as communicated in the FDA's guidance– Dry Eye: Developing Drugs for Treatment . Therefore, improvement in DE symptoms will also be evaluated as a co-primary endpoint to determine whether there is an added benefit of NGF in severe Sjogren's DE.

### 2.3.1. Risk assessment/benefit evaluation

This study is considered a low-risk interventional trial. It is conducted with a previously tested dose of medicinal product already authorized and commercialized for the treatment of NK in Europe, US and China. The proposed study is conducted in patients with severe Sjogren's DED, under treatment with CsA administered as clinical practice under authorized indication. Sjogren's DED is an indication for which Oxervate® (cenegermin) ophthalmic solution is not yet approved, however two preliminary clinical studies were already conducted in patients with DE demonstrating that cenegermin is well tolerated in this condition. The risk of this study is comparable to the risk of the standard of care, in fact the dose proposed in this protocol is cenegermin 20 mcg/mL three drops per day instilled in each eye, which is well below the dose approved for the treatment of NK (cenegermin 20 mcg/mL six drops/eye per day).

In particular, based on the approved Oxervate® SmPC the interactions with other drugs might be reduced if cenegermin is administered first, using 15 minutes apart, with the exception of agents known to inhibit epithelial healing (e.g. corticosteroids or eye drops containing preservatives such as benzalkonium chloride, polyquaternium-1, benzododecinium bromide, cetrimide and other quaternary ammonium derivatives). As systemic absorption of cenegermin after use of the medicinal product is negligible or not detectable, no drug interactions are anticipated.

On top of the above, in ciclosporin SmPC (brand name IKERVIS) is described that no interaction studies have been performed with IKERVIS and combination with other medicinal products that affect the immune system co-administration of IKERVIS with eye drops containing corticosteroids could potentiate the effects of ciclosporin on the immune system.

Based on these SmPCs description, and because no corticosteroids are administered, no interactions are expected in this clinical trial.

Considering what is discussed above, no particular safety risks are foreseen with respect to the safety profile of the marketed product Oxervate® (cenegermin 20 mcg/mL ophthalmic solution).

The patients with severe Sjogren's DED participating in this study may potentially benefit from the application of cenegermin for 28 days (4 weeks).

Any possible risk derived from the administration of cenegermin in the specific population involved in this study will be minimized by integrated monitoring which includes clinical observations, Ocular examination, laboratory tests.

# **2.3.2.** Description of the Investigational Product

The investigational medicinal product (IMP) consists of a sterile isotonic solution for ophthalmic administration, containing cenegermin 20 mcg/mL as drug substance.

The matching placebo consists of the vehicle of cenegermin (sterile isotonic solution).

Further information is given in section 5.

# 3. OVERALL STUDY DESIGN AND INVESTIGATIONAL PLAN

# **3.1. STUDY OBJECTIVES**

The study objective is to assess the efficacy and safety of cenegermin (rhNGF) ophthalmic solution at 20 mcg/mL concentration administered TID for 4 weeks in patients with severe Sjogren's DED who are under treatment with topical Cyclosporine A (or other drugs of the same class).

### **3.2.** STUDY ADMINISTRATIVE STRUCTURE

This study will be performed at approximately 10 study centers located in the USA and Europe. At each study center, the Principal Investigator (PI) will be responsible for ensuring that the investigation is conducted according to the signed Investigator agreement, the protocol, GCP guidelines, and local regulations.

The PI at each study center will be responsible for the management of the study, which will consist of maintaining the study file and the patient records, corresponding with the IRB/EC, completing the electronic case report forms (eCRFs) and reporting SAEs within 24 hours of initial awareness.

The PI is responsible for supervising any individual or party to whom the investigator delegates trial related duties and functions conducted at the trial site.

If the investigator/institution retains the services of any individual or party to perform trial-related duties and functions, the investigator/institution should ensure this individual or party is qualified to perform those trial-related duties and functions and should implement procedures to ensure the integrity of the trial-related duties and functions performed and any data generated.

### **3.3. OVERALL STUDY DESIGN**

This is a 4-week phase III, multicenter, double-masked, vehicle-controlled study to evaluate safety and efficacy of cenegermin ophthalmic solution at 20 mcg/mL solution versus vehicle, in patients with severe Sjogren's DED who are under treatment with topical Cyclosporine A (or other drugs of the same class). Patients will be evaluated as per Section 2 "SCHEDULE OF EVALUATIONS".

During the screening (day-8) all procedures for inclusion will be performed. From the day of screening the patients will stop any kind of further treatment, except CsA and commercially available preservative free artificial tears provided by Sponsor for a period of 8 days and 10 days as maximum: day -8 until the baseline visit (day 1+2); Figure 1. At the end of the wash out period (day -8 to baseline), patients meeting the entry criteria for this study will be randomized 1:1 and treated for 4 weeks with either cenegermin ophthalmic solution 20 mcg/mL TID or vehicle TID.

In addition to topical CsA eye drops (both groups will continue with topical CsA eye drops, or other topical ophthalmic treatment of the same class, as previously prescribed), during the 4 weeks of masked treatment only the administration of IMP is allowed. Nevertheless, if strictly needed, the patient can take preservative

free artificial tears (provided by the Sponsor). The use ( $n^{\circ}$  drops/day) of preservative free artificial tears will be clearly documented in a patient's diary and in the eCRF.

Eight weeks post treatment with no further topical ocular treatment except CsA and commercially available preservative-free artificial tears provided by the Sponsor TID will follow the completion of the double-blind treatment. During this follow up period, the patient can administer additional preservative-free artificial tear eye drops, provided by Sponsor, only if strictly needed, and must document in the patient's diary the number of additional drops administered for each eye.

Patients will then be followed up for efficacy and safety endpoints until week 16 and for safety endpoints until week 24. During the follow up period after week 12 until week 24 other topical treatments, in addition to CsA, will be allowed at discretion of the treating physician. Such treatments will be recorded by the investigators. Throughout the study, the patient can continue any systemic treatment as required to control their autoimmune disease, and any change in systemic treatments must be recorded by the investigators. The total duration of the study is 25 weeks including 1 week of screening.

[figure not shown]

Figure 1. Study duration

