- **10.** Any concurrent medical condition, that in the judgment of the PI, might interfere with the conduct of the study, confound the interpretation of the study results, or endanger the patient's well-being
- **11.** Use of topical corticosteroids, lifitegrast, autologous serum tears in either eye during the study (previous use not an exclusion criteria but must be discontinued at the screening visit)
- 12. Contact lenses, True Tear device, moisture goggles, sutureless amniotic membrane or punctum plug use during the study (previous use not an exclusion criteria but must be discontinued at the screening visit)
- 13. History of drug addiction or alcohol abuse in the last 2 years
- **14.** Any prior ocular surgery (including refractive, palpebral and cataract surgery) if within 90 days before the screening visit

- **15.** Participation in a clinical trial with a new active substance during the past 3 months
- **16.** Participation in another clinical trial study at the same time as the present study.

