## 5.6. CONCOMITANT MEDICATION

As a general rule, in addition to the standard chronic treatment with topical CsA (or other ophthalmic treatment of the same class) that will not be discontinued to participate in the study, no ophthalmic medication other than study drug will be given to the patient from the screening day until all of the final study evaluations have been completed, except for preservative free artificial tears provided by the Sponsor.

IMP should be administered first and concomitant medications should be administered as follows:

- Topical CsA eye drops (or other topical ophthalmic treatment of the same class) as previously prescribed at least 15 minutes apart
- Preservative free artificial tears provided by the Sponsor at least 15 minutes apart

The preservative free artificial tears will be provided by the Sponsor and can be used according to the following scheme:

- 1) During the 4 weeks of masked treatment, only if strictly needed, the patient will instill one drop in both eyes.
- 2) During the 8 weeks of Follow-up period post-treatment one drop will be instilled in both eyes TID (morning, afternoon and evening).

The use (n° drops/day) of preservative free artificial tears will be clearly documented in the patient's diary and eCRF.

All medications (including over-the-counter drugs, herbal products, vitamins, and antacids) taken within 4 weeks prior to the start of and throughout the study will be clearly documented on the Concomitant Medications eCRF page.

Medication entries should be specific to product name (if a combination drug product) and spelled correctly. The dose, unit, frequency, route of administration, start date, discontinuation date, and indication should also be recorded. For medications administered only one time, the frequency column may reflect "once."

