## 6.2. STUDY VISITS AND FOLLOW-UP ASSESSMENTS

After the first two weeks of treatment the patient will undergo a medical assessment during the visit 2 (week 2).

Following the completion of the double-blind treatment (visit 3, week 4), patients will be followed up for efficacy until visit 6 (week 16) and safety assessments until visit 7 (week 24) During the follow-up period until week 12 patients will not use further ophthalmic treatment except CsA and preservative free artificial tears, provided by Sponsor, one drop instilled in both eyes three times daily (morning, afternoon and evening). The patient, only if strictly needed, can administer additional drops and must document in the patient's diary the n° of additional drops administered for each eye. After week 12 (visit 5), patients will be followed-up for additional 12 weeks until the end of the study (visit 7, week 24) during which patients can use CsA and others artificial tears different from the artificial tears provided by the Sponsor.

Slit lamp examination and the fluorescein staining (Corneal and/or Conjunctival staining with Fluorescein) will be performed at different time-points, as specified in the section 2 of "SCHEDULE OF EVALUATIONS" and procedure will be detailed on the informed consent form.

An independent Blinded Reading Center will also be used to assess the images collected, as described in the previous paragraph.

	Day	Procedures/Assessments
At home	Days 1-14 ±2	
 
Self-administration at home of the IMP, three times daily every 6 h for both eyes (diary)
 
Recording any new or changes in concomitant medications (diary)
 
Recording any unusual medical conditions - AE monitoring (diary)
 
Recording possible use of preservative free artificial tears (diary).
 
Data will be recorded by the patient in the patient's diary.
 

	Day	Procedures/Assessments

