Visit 5 Follow up week 12	Day 84 ± 4	
 
The following procedures will be performed (the below order is mandatory):
 
> Ocular examination of both eyes to be performed by the physician investigator: 
 
Assessment by SANDE questionnaire
 
Assessment of best corrected distance visual acuity (BCDVA)
 
External Ocular Examination
 
Schirmer test I (without anesthesia)
 
Slit-lamp examination (SLE) to assess the Eyelid - Meibomian glands, Eyelid - Erythema, Eyelid - Edema Lashes, Conjunctiva Erythema, Lens, Iris, Anterior Chamber, Corneal Horizontal Diameter
 
TFBUT
 
Ocular surface staining (NEI score - corneal and conjunctival fluoresce instaining)
 
 
 
> Concomitant ocular and systemic medications
 
> Frequency of patient's artificial tear use during 4 weeks of FU (to be reported in eCRF).
 
> AE monitoring
 
During visit 5, week 12, PI or delegate must check and collect the patient's diary concerning the follow up period and provide a new diary for the second follow up period.
 
The Investigator will instruct the patient that during the follow up period (from week 13 to week 24) other topical treatments will be allowed at discretion of the treating physician. Such treatments will be recorded by the investigators. The patient has to register the use other preservative free artificial tears in the patient's diary.
 

At home	Day 84 ± 4– 168 ± 7	
 
Recording any new or changes in concomitant medications (diary)
 
Recording any unusual medical conditions - AE monitoring (diary)
 
Artificial tears use during 4 weeks of FU (diary)
 
Data will be recorded by the patient on the patient's diary.
 

	Day	Procedures/Assessments

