# Objective(s)

- To compare the efficacy of cenegermin vs. vehicle in Cornea and conjunctiva vital staining with fluorescein (National Eye Institute [NEI] scales) at week 4, 8, 12 and 16 by testing the superiority.
- To compare the efficacy of cenegermin vs. vehicle in Tear Film Break-Up Time (TFBUT) at week 4, 8, 12 and 16 by testing the superiority.
- To compare the efficacy of cenegermin vs. vehicle in SANDE scores at week 8, 12 and 16 by testing the superiority.
- To compare the efficacy of cenegermin vs. vehicle in worsening in symptom scores (SANDE) and/or NEI score at week 4 by testing the superiority.
- To compare the efficacy of cenegermin vs. vehicle in impact of dry eye on everyday life (IDEEL) questionnaire at week 4, 8, 12 and 16 by testing the superiority.

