7.2.6 Per Protocol set (PP)

The PP set will consist of all randomized patients who received at least one dose of the investigational product and do not have Major Protocol Deviations. The PP population will be used for sensitivity analyses.

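### The protocol contradicts itself on eye treatments in weeks 13-24, and a late deviation classed as major can remove clean week-4 and week-12 data from the per-protocol analyses

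*Protocol*

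**What the plan says.** On eye treatment after week 12 the protocol takes several positions.

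- **Allowed at discretion.** Section 3.3: "after week 12 until week 24 other topical treatments, in addition to CsA, will be allowed at discretion of the treating physician". The synopsis and SAP section 3.3 say the same. The Visit 5 row of section 6.2 tells the investigator to inform the patient that "other topical treatments will be allowed at discretion of the treating physician".
- **Barred.** Section 5.6 exempts CsA (or its class) and sponsor-supplied tears, and otherwise states, as a general rule, that "no ophthalmic medication other than study drug will be given to the patient from the screening day until all of the final study evaluations" are complete. Section 6.1 stops all other ophthalmic treatment to the same end point, exempting CsA and preservative-free tears, and without the general-rule qualifier.
- **Named agents barred.** Exclusion criterion 11: "Use of topical corticosteroids, lifitegrast, autologous serum tears in either eye during the study". Earlier use is acceptable if stopped at screening. No week-12 limit is given.
- **Narrower permission.** The opening text of section 6.2 describes the period to week 24 as one "during which patients can use CsA and others artificial tears different from the artificial tears provided by the Sponsor". It mentions no other treatment.

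The risk assessment in section 2.3.1 adds that "because no corticosteroids are administered, no interactions are expected in this clinical trial".

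On analysis, SAP section 7.2.6 limits the PP set to treated, randomised patients who "do not have Major Protocol Deviations"; protocol section 9.2 agrees. Neither gives a time limit or a list of major deviations. SAP section 8.2 has deviations discussed case by case at the blind data review. SAP section 7.9 replaces the protocol's two locks with one at study end. SAP section 3.2.2 lists week 16 among its superiority objectives, for example "To compare the efficacy of cenegermin vs. vehicle in SANDE scores at week 8, 12 and 16 by testing the superiority".

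**The concern.** A site cannot comply with all of these passages. One site may record a drop started in week 13 as permitted treatment and another may record it as a deviation.

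This reaches the analysis through the PP set. Membership is decided per patient, not per endpoint, and both co-primary values are recorded by Visit 5. A deviation after that visit cannot have influenced either value, yet it can remove both. Add-on treatment is plausibly more common in patients who are doing badly, so such removals need not be random with respect to outcome or arm.

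Two lesser points follow. The week-16 comparison is made after the permissive passages open up add-on treatment, so a reader needs to know how much was used in each arm. And the premise in section 2.3.1 that no corticosteroids are given is not assured under the permissive passages.

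**Working it through.** **Step 1. Put two examples through each passage.** Both are started just after Visit 5.

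| Passage | Non-sponsor preservative-free tears | Topical corticosteroid |
|---|---|---|
| Protocol 3.3, synopsis, Visit 5, SAP 3.3 | allowed | allowed at discretion |
| Protocol 6.2, opening text | allowed | not mentioned |
| Protocol 6.1 | allowed | barred |
| Protocol 5.6 | barred (only sponsor tears exempt) | barred |
| Exclusion criterion 11 | silent | barred |

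Both examples give conflicting answers. Reading the final study evaluations as the last efficacy visit (week 16) does not remove the conflict: weeks 13-16 would still be covered by both rules, and that is the interval before the week-16 measurement.

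**Step 2. Trace the route to the PP set.** Schirmer I is read at week 4 (day 28 ± 2) and SANDE at week 12 (day 84 ± 4, Visit 5). Follow-up runs to week 24 (day 168 ± 7). Protocol section 9.3 planned a lock of data up to week 12 for the main analysis. Under SAP section 7.9 there is one lock after week 24, and SAP section 7.10 puts the blind review before it. Deviations from weeks 13-24 are therefore known when PP status is set, and SAP section 7.2.6 does not exclude them from that decision.

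**Step 3. Reproduce the plan's power.** Inputs from SAP section 5: 36 per arm, one-sided alpha 0.025, responders 33% vs 75%, SANDE difference 10 with SD 12.

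- Schirmer I, pooled normal test: mean rate 0.54; null SE = √(2 × 0.54 × 0.46 / 36) = 0.1175; alternative SE = √((0.33 × 0.67 + 0.75 × 0.25) / 36) = 0.1065. Power = Φ[(0.42 − 1.96 × 0.1175) / 0.1065] = Φ(1.78) = 96.3%. Stated: 96.3%.
- SANDE: 10 / (12 × √(2/36)) = 3.54; Φ(3.54 − 1.96) = 94.2% (noncentral t: 93.7%). Stated: 94.1%.
- Joint, assuming independence: 0.963 × 0.937 = 90.2%. Stated: 90%.

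**Step 4. Illustrate PP loss.** The documents give no rate of late deviations, so the range below is assumed. It takes exclusions balanced by arm, SAP effect sizes, the t version for SANDE, and independence.

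| Removed | Per arm | Schirmer I | SANDE | Joint | SE ratio |
|---|---|---|---|---|---|
| 0% | 36 | 96.3% | 93.7% | 90.2% | 1.00 |
| 10% | 32 | 94.0% | 90.7% | 85.2% | 1.06 |
| 20% | 29 | 91.6% | 87.7% | 80.3% | 1.11 |
| 30% | 25 | 87.0% | 82.3% | 71.6% | 1.20 |
| 40% | 22 | 82.1% | 77.0% | 63.3% | 1.28 |

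This shows lost precision only. Unbalanced, outcome-related removal would also shift the PP estimate. The documents do not allow that shift to be sized.

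**The case against.** The strongest reply is that little depends on this.

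- *The co-primary analyses are safe.* Correct. They use the FAS by allocated treatment (SAP sections 7.2.4 and 7.4), and PP is supportive (SAP section 10.1.4).
- *Only major deviations exclude a patient, and grading is masked.* Correct. SAP section 3.3 itself describes these treatments as allowed, so the review might well not grade them as major. But no criteria are written down, and the protocol passages that bar treatment would support the opposite grading.
- *The contradiction is softer than it looks.* Partly. The opening of section 6.2 is permissive and does not say that nothing else may be used. The general-rule wording in section 5.6 leaves room for an exception, and section 6.1 attaches a wash-out gloss to its restriction. But section 6.1 still runs to the end of final evaluations, and exclusion criterion 11 has no exception after screening.
- *The safety premise concerns the treatment period.* Largely fair: study drug stops at week 4. CsA continues, however, and section 2.3.1 also refers to labelling on steroids given with ciclosporin.

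A reader might go further on week 16 and infer that a confirmatory superiority claim is biased with nothing in place to deal with it. The documents do not support that. The ranked tests stop at week 12 (SAP sections 10.2.1 and 10.2.2), SAP section 10.2.3 makes the week-16 comparisons descriptive, and the FAS follows a treatment-policy strategy, under which values after add-on treatment are used by design. Nor is persistence a stated objective; it appears only in the background and rationale.

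A reader might also take the 13-14 point steroid benefit in protocol section 9.1 and compute attenuation: 13.5 × 0.10 = 1.4 points up to 13.5 × 0.40 = 5.4 points, or 14% to 54% of a 10-point effect. That needs a steroid-sized benefit for every add-on, a 10-point difference still present at week 16, and an uptake imbalance of 10 to 40 percentage points. None of these is given.

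**Conclusion.** The point holds as a conflict in the rules of conduct with a limited statistical consequence. For weeks 13-24 the same eye treatment is permitted by some passages and barred by others. Because PP status has no time limit and is set before one end-of-study lock, a post-week-12 deviation classed as major can discard valid co-primary values from the supportive PP analyses.

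The size cannot be fixed from the documents. Under the assumed balanced losses, joint PP power stays near 85% with 10% removed and falls to about 63% with 40% removed. It rests on late deviations occurring and being graded as major, which the plan neither predicts nor rules out.

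The FAS co-primary analyses, their power and their type I error are unaffected. Week 16 is a matter of labelling and interpretation, not of error control.

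**What to change.** 1. **Protocol and SAP section 3.3.** Reconcile the synopsis, section 2.3.1, section 3.3, exclusion criterion 11, sections 5.6 and 6.1, the opening of section 6.2, the Visit 5 instructions and SAP section 3.3 into one statement for weeks 13-24. It should make clear which uses count as deviations. Which rule is right is a clinical decision for the sponsor and is not addressed here.
2. **SAP section 7.2.6.** Define PP status per endpoint: major deviations up to the week-4 assessment for Schirmer I, and up to the week-12 assessment for SANDE.
3. **SAP section 3.2.2.** Label the week-16 comparisons as descriptive, in line with SAP section 10.2.3.
4. **SAP section 8.6.** Add a table by arm of new topical eye treatments started between Visit 5 and Visit 6. The planned concomitant-medication tables cover everything taken after first dose and do not isolate this window.

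Discarding week-16 values after add-on treatment should not be part of the change: it would remove patients selectively, possibly differently by arm.

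The cost is clarified wording, one extra table and two PP flags instead of one. Sample size and the primary analysis do not change.
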